7.2.3 Cardiac CT/MRA subset

An additional subset of study subjects will be enrolled in the cardiac CT/MRA subset and undergo a 3-month CT/MRA in addition to the baseline CT/MRA (all subjects will have a baseline CT/MRA) to assess incidence of post-ablation PV stenosis. A total of 30 subjects will be included in the CT/MRA subset at sites that have the appropriate equipment for CT/MRA imaging.

In addition to this subset, any subjects with signs or symptoms of PV stenosis will undergo a post ablation CT/MRA. These subjects will not be included in the CT/MRA subset analysis. If severe PV stenosis is present, it will be reported as adverse event. The CT/MRA data will be analyzed for PV stenosis by an independent Core Laboratory.

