7.2.4 PVI Durability Subset

A subset of 30 study subjects will be enrolled in the PVI Durability subset and will, in addition to the index ablation procedure and general follow up schedule, undergo an electro-anatomical re-map procedure at 75 days (+/- 15days) post index ablation procedure. The re-map is intended to evaluate the durability of the pulmonary vein isolation generated at the index ablation procedure. The assessment of lesion durability will be done by the ablating physician at the participating sites.

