13.4 Repeat Ablation Procedures

Repeat procedures may be performed at the discretion of the investigator. It is highly recommended to collect arrhythmia documentation (in example documented recurrences) before performing a repeat procedure.

Repeat procedures **during the blanking period** (\leq 90 days post index ablation procedure) must be conducted with the investigational device, with or without focal touch-up, if the arrhythmia is due to PV triggers. If the arrhythmia is due to non-PV triggers and the subject is treated with a commercially available ablation catheter and generator, the subject will be excluded from the long- term effectiveness cohort. Procedures for CTI dependent flutter in the follow up period are not considered repeat procedures per CIP.

Repeat procedures performed **after the blanking period** (\geq 90- 365days post index ablation procedure) may be managed per investigator discretion using a commercially available ablation catheter and generator.

For the repeat procedures, the investigator must collect and provide information on location of reconnections of PVs and in case of atrial flutter recurrence, confirm if CTI dependent flutter or not. The follow-up schedule will remain based on the index ablation procedure.

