13.5.2 Monthly follow-up visit

At 1, 3, 6 and, 12-month follow-up visits, the following assessments will be performed:

- **Medical evaluation:**
 - AEs
 - Cardiac and anti-coagulation medication regimen
 - Cardiac related hospitalization and cardioversions
 - 12 Lead-ECG
- **As from 1-month: Atrial arrhythmia monitoring (non-SOC)**
 - **Remote Monitoring:** subjects will be provided with a remote monitoring device at the 1M FU visit and asked to record and transmit a minimum of 1 transmission (≥ 30 seconds) every week through the end of the month 5 of FU. Starting at month 6 of FU, subjects will be asked to record and transmit a minimum of 1 transmission (≥ 30 seconds) every month until the effectiveness evaluation period is completed (12 months post index ablation procedure). Subjects will also be asked to transmit any symptom-triggered episode that occurs from the time they receive the remote monitoring device through the 12M FU visit. Remote monitoring will be **conducted as follows:**
 - Distribution and start by month 1
 - <6 M: Weekly transmission of at least 1 scheduled recording
 - ≥ 6 M: Monthly transmission of at least 1 scheduled recording
 - Conduct and transmit recording whenever symptoms are present
 - **24 Hour Holter Monitoring:** per CIP a Holter monitor will be used at the 3-, 6- and 12-months follow-up visit to monitor the subjects' heart rhythm for 24 hours continuously. Following the 24h Holter, subjects will be contacted by the site to verify if symptoms are experienced during 24h Holter. An independent core laboratory will be used to evaluate and assess the remote and 24h Holter monitoring tracings.
- Additional Assessments for Cardiac **CT/MRA** subset subjects: A **cardiac CT/MRA** is required to be performed at the 3M FU (non-SOC) visit or any other point in time when the subject presents with symptoms of PV stenosis. For other subjects, a cardiac CT/MRA is only required to be performed if the subject presents with symptoms of PV stenosis.
- Additional Assessments for **NA** subset subjects (non-SOC): A **Cerebral MRI, Neurological Exam and Neurological Evaluation using the MMSE, NIHSS and mRS** are required to be performed if any neurological symptoms and/or cerebral ischemic lesions were identified at a prior evaluation.
NOTE: Patient questionnaires will only be used in countries with validated languages.

- Additional Assessments for **PVI Durability subset** subjects (non-SOC):

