- **Cardiac CT/MRA Analysis Set:** The CT/MRA analysis set will include all CT/MRA subset subjects who have readable outcomes at both baseline and 3 months visit.
- **PVI Durability Analysis Set:** The PVI durability analysis set will include all durability subset subjects who have readable electro-anatomical mapping at the index ablation procedure and have the mapping 75 days (+/-15 days) post index ablation procedure.

Note that discontinued subjects are not subjected to the additional subset assessments (NA, EE, CT/MRA, and PVI durability).

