### 7.12.1 Analysis of PVI Durability Endpoint

Percentage of targeted PVs in the index ablation procedure being durably isolated as confirmed by the electroanatomical mapping 75 days (+/- 15 days) post index ablation procedure.

Percentage of subjects with durably isolated targeted PVs, as confirmed by the electroanatomical mapping at 75 days (+/- 15 days) post index ablation procedure.

These analyses will be performed in the PVI Durability Analysis Set.

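### PVI durability is judged from the Day 75 map alone, so a vein already found reconnected at an earlier repeat ablation is lost or can be scored durable; CT/MRA has a smaller gap of the same kind

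*SAP*

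**What the plan says.** **Durability.** SAP section 5 admits "all durability subset subjects who have readable electro-anatomical mapping at the index ablation procedure and have the mapping 75 days" (±15) after the index procedure. Protocol 19.3 sets the same two-map condition. SAP 7.12.1 defines the vein-level endpoint as "Percentage of targeted PVs in the index ablation procedure being durably isolated as confirmed by the electroanatomical mapping 75 days" and the subject-level endpoint as "Percentage of subjects with durably isolated targeted PVs, as confirmed by the electroanatomical mapping at 75 days (+/- 15 days) post index ablation procedure". Protocol 7.2.4 gives the size ("A subset of 30 study subjects will be enrolled in the PVI Durability subset") and says that the re-map is meant to judge the isolation produced at the index procedure.

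**Repeat ablation.** Protocol 13.4 leaves repeat procedures to the investigator. Up to Day 90, a repeat for PV triggers must be done with the investigational device. At any repeat, "the investigator must collect and provide information on location of reconnections of PVs". Protocol 13.5 keeps the visit schedule tied to the index procedure. SAP 7.1.4 has rules for durability subjects ablated at the re-map visit, and only for the repeat-procedure and long-term effectiveness analyses.

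**CT/MRA.** SAP section 5 admits "all CT/MRA subset subjects who have readable outcomes at both baseline and 3 months visit". Protocol 7.2.3 gives the size: "A total of 30 subjects will be included in the CT/MRA subset". Protocol 13.5.2 asks subset subjects for a scan at the 3-month "visit or any other point in time when the subject presents with symptoms of PV stenosis". The endpoint (protocol 7.3.4, SAP 7.12.3) covers stenosis at any time up to 3 months.

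**The concern.** A durable isolation is one that has not failed by the time of the re-map. A vein found reconnected at a repeat ablation has already failed, but neither the set nor the endpoint uses that finding. What happens to the subject depends on whether a Day 60–90 map is made later, and either outcome helps the device: the subject disappears from the denominator, or is mapped after the vein has been re-isolated.

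At stake is the accuracy of a descriptive durability rate from a set of 30. Under SAP 7.12 that rate goes into the 3-Month CSR, which is part of the CE mark dossier. The study is single-arm, and under protocol 7.2.4 the ablating physician makes the durability assessment, so the scoring rule should be fixed in advance.

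**Working it through.** The plan states no expected rate or precision for either subset, so there is no figure to reproduce. The check is a reading of the rules, followed by an illustration of size.

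**Step 1: follow one subject.** The re-map window is 75 − 15 = Day 60 to 75 + 15 = Day 90. Suppose that a subset subject has an early recurrence, a targeted vein is found reconnected before Day 60, and it is re-isolated with the study device as protocol 13.4 requires for PV triggers.

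- No map in Day 60–90: the subject fails set entry (SAP 5).
- Map in Day 60–90 with all targeted veins isolated: nothing in SAP 5 or 7.12.1 stops the subject and the vein from being counted as durable.
- SAP 7.1.4 does not apply, because the ablation was not at the re-map visit.

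**Step 2: subject-level size.** Let d of 30 subjects be truly durable, and let k of the remaining 30 − d be re-ablated early. The counts d and k are assumptions.

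- Correct rate: d/30
- Subjects dropped: d/(30 − k)
- Subjects scored after re-isolation: (d + k)/30

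| Correct | k = 1, dropped | k = 1, re-scored | k = 3, dropped | k = 3, re-scored |
|---|---|---|---|---|
| 18/30 = 60.0% | 18/29 = 62.1% (+2.1) | 19/30 = 63.3% (+3.3) | 18/27 = 66.7% (+6.7) | 21/30 = 70.0% (+10.0) |
| 21/30 = 70.0% | 21/29 = 72.4% (+2.4) | 22/30 = 73.3% (+3.3) | 21/27 = 77.8% (+7.8) | 24/30 = 80.0% (+10.0) |
| 24/30 = 80.0% | 24/29 = 82.8% (+2.8) | 25/30 = 83.3% (+3.3) | 24/27 = 88.9% (+8.9) | 27/30 = 90.0% (+10.0) |
| 27/30 = 90.0% | 27/29 = 93.1% (+3.1) | 28/30 = 93.3% (+3.3) | 27/27 = 100% (+10.0) | 30/30 = 100% (+10.0) |

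Each case adds 2.1 to 3.1 points if dropped and 3.3 points if re-scored. For scale, the exact 95% interval at 24/30 is 61.4% to 92.3%.

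**Step 3: vein-level size.** Assume 4 veins per subject (120 in all), 1 or 2 of them reconnected in each early-repeat subject, and a true rate of 80% or 90%. One subject with one reconnected vein moves 96/120 = 80.0% to 93/116 = 80.2% if dropped, or to 97/120 = 80.8% if re-scored. Across these assumptions, three such subjects add about 0.6 to 5.0 points.

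**Step 4: CT/MRA.** Suppose that one of 30 subjects has stenosis on an early scan and no readable 3-month scan. Then 1/30 = 3.3% (exact 95% upper bound 17.2%) becomes 0/29 = 0% (upper bound 11.9%).

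**The case against.** **The stated purpose already excludes such veins.** Protocol 7.2.4 ties the re-map to the isolation made at the index procedure, and a vein known to have reconnected does not meet that aim. This stands in part. A reader might infer that the plan directs re-isolated veins to be counted as durable, but no text says so. What exists is a missing rule that leaves that scoring open. The purpose statement also does nothing for the subject who has no in-window map.

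**The findings are reported elsewhere.** SAP 7.11.3 tabulates reconnection at repeat procedures by vein and by subject, so the data are not hidden. But that summary is planned only after 12-month follow-up, while durability is reported in the 3-Month CSR.

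**Early repeats may be rare.** Subset subjects already have an invasive re-map scheduled, and protocol 13.5.2 allows ablation at it. This stands: the frequency is unknown and may be zero.

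**CT/MRA is largely covered.** A reader might infer that early stenosis in this subset is generally lost, or that entry depends on the outcome as it does for durability. The documents do not support that. The endpoint runs up to 3 months, so an early positive scan with a readable 3-month scan can already be counted. Loss needs an early positive scan together with a missing or unreadable 3-month scan, and nothing in the plan makes those go together beyond the alternative wording in protocol 13.5.2. Severe stenosis (at least 70% diameter reduction) up to Day 90 is a primary adverse event (protocol 14.1.3) and counts whatever the follow-up length (SAP 7.8.1). Only lesser stenosis lacks that second route.

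**Commercial completion.** A reader might also infer that veins completed with a commercial catheter inflate durability, and that the count should be limited to veins isolated with the study device. SAP 7.1.3 treats completion for study-system reasons as acute failure. At the planned 97% acute success rate, that is about 0.03 × 30 = 0.9 subject. Limiting the count would remove the veins that the device failed to isolate, which can itself raise the rate.

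**Conclusion.** The durability gap is real. A targeted vein found reconnected at a repeat ablation before the re-map has no scoring rule, and both ways of handling it that the text leaves open favour the device. The size is about 2 to 3 points on the subject-level rate per such subject, assuming 30 subjects, true durability of 60% to 90%, and, on the re-scored route, that all targeted veins are isolated at the later map. The number of such subjects is not in the documents, so the total effect cannot be stated.

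The CT/MRA gap is minor: the set definition is narrower than the endpoint it serves, and severe cases to Day 90 are still counted in the primary safety analysis.

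Both endpoints are descriptive, with no hypothesis or success rule (protocol 19.4.6, SAP 7.11). No primary or secondary conclusion changes. The wording should be settled before the 3-Month CSR.

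**What to change.** **SAP 5 and 7.12.1, protocol 19.3.** State that a targeted PV found reconnected at any repeat procedure before the re-map counts as not durably isolated, and that the subject stays in the set as not durable, whether or not a later map exists. Carry forward reconnections only. A vein found isolated at an early repeat still needs its Day 60–90 map.

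**SAP 5 and 7.12.3, protocol 19.3.** Keep in the set, as an event, any CT/MRA subset subject with core-lab stenosis on a post-ablation scan up to the 3-month visit. An early negative scan does not replace the 3-month scan.

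Leave the vein count on all targeted PVs.

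**Cost.** Wording only. Protocol 13.4 already requires the location of reconnections, and protocol 13.5.2 already calls for symptom-driven scans, so no new test or visit is needed. The reported durability rate may be slightly lower and the stenosis rate possibly higher.

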## 6. Sample Size Justification

- **Primary Safety Endpoint:**

Based on a performance goal of 12% and assuming an anticipated primary safety event rate of 5% for the primary safety endpoint, a sample size of 135 subjects (with 5% missing data due to attrition) will provide above 80% power to reject the null hypothesis for the primary safety hypothesis test using a one-sided exact binomial test. The target significance level is 0.025.

- **Primary Effectiveness Endpoint:**

Based on a performance goal of 90% and assuming an anticipated failure-free rate of 97% for the primary effectiveness endpoint, a sample size of 100 subjects will provide

more than 80% power to reject the null hypothesis for the primary effectiveness endpoint using a one-sided exact binomial test. The target significance level is 0.025.

- **Secondary Effectiveness Endpoint:**

Based on a performance goal of 50% and assuming an anticipated failure-free rate of 65% for the secondary effectiveness endpoint, a sample size of 100 subjects (with 10% missing data due to attrition) will provide above 80% power to reject the null hypothesis test for the secondary effectiveness hypothesis using a one-sided exact binomial test. The target significance level is 0.025.

- **Total Sample size:**

The sample size of this study is mainly driven by the hypothesis test for the primary safety endpoint. The total sample size for this study will be 135 subjects, based on the 135 subjects needed for the primary safety endpoint evaluation, 100 subjects for the primary acute effectiveness endpoint evaluation, and 100 subjects for the secondary effectiveness endpoint evaluation. The sample size estimation assumes a 5% attrition rate of the subjects for the primary safety endpoint and no and 10% attribution of the subjects for the primary and secondary effectiveness endpoints, respectively.

## 7. Statistical Analysis Methods

### 7.1 General Conventions

#### 7.1.1 Descriptive Statistics

Standard descriptive summaries for continuous data include the number of observations (e.g., subjects, veins, applications of ablation, etc.) with available data, mean, standard deviation, median, 25% percentile, 75% percentile, minimum, and maximum values will be presented. For categorical data, the count and percent will be provided. Percentages will be based on the number of observations without missing data.

#### 7.1.2 Handelling Discontinued Subjects in Effectiveness Endpoint Analysis

For all effectiveness endpoints, subjects who are **discontinued** (no energy delivered with the study catheter/system) due to:

- Study system (SMARTTOUCH™ SF (STSF) and TRUPULSE™ Generator) related reasons will be considered acute effectiveness failures.
- Non-study system related reasons (e.g., pump, other equipment or anatomy that precludes treatment with THERMOCOOL SMARTTOUCH™ SF (STSF) Catheter and TRUPULSE™ Generator or a commercially available device) will be deemed as missing the outcome of the acute effectiveness endpoint and excluded from the long-term effectiveness endpoint analyses, including the secondary endpoint.

### 7.1.3 Handelling Subjects with Specific Ablation Scenarios in Effectiveness Endpoint Analysis

Subjects who undergo ablation using the investigational ablation system or commercial ablation devices at the **PV/CTI regions or outside the PV/CTI regions** will be included in the analysis of acute and long-term effectiveness endpoints according to the following guidelines:

- Condition 1: Subjects who undergo ablation **using the investigational ablation system for PV isolation** will be included in the analysis of acute effectiveness endpoints.
  - If the PV isolation is completed using commercial RF (radiofrequency) devices due to reasons related to the study system (SMARTTOUCH™ SF (STSF) and TRUPULSE™ Generator), the subject will be considered a failure for the acute effectiveness endpoint and be included in acute and long-term effectiveness endpoint analyses..
  - If the PV isolation is completed using commercial RF devices due to reasons unrelated to the study system (SMARTTOUCH™ SF (STSF) and TRUPULSE™ Generator), the subject will be considered not evaluable for the effectiveness of the investigational system and will be excluded from the analyses of acute and long-term effectiveness endpoints.
- Condition 2: The use of the **investigational ablation system outside the PV/CTI region is not permitted** according to the protocol. Subjects who undergo ablation outside the intended regions using investigational ablation system will be excluded from the long-term effectiveness endpoint analysis, unless they have already failed the acute effectiveness endpoint. Subjects who failed the acute effectiveness endpoint will also be considered failures for the long-term effectiveness endpoint.

- Condition 3: In cases where **commercial RF devices are used for ablation outside the PV region and/or CTI line** to treat arrhythmia identified during the procedure, it is allowed for the well-being of the patient. However, these subjects will be excluded from the long-term effectiveness analysis, as they received additional ablations beyond the intended treatment using non-investigational devices. This exclusion is necessary to avoid mixed effects from non-study devices that could confound the interpretation of the long-term effectiveness results for the investigational devices.
- Condition 4: The **use of the investigational ablation system or commercial RF devices for the ablation of the CTI line to treat documented typical atrial flutter**, identified prior to or during the procedure, is allowed. As the investigational devices are the primary devices used for PV region ablation, these subjects who undergo CTI line ablation will be included in the analyses for acute and long-term effectiveness endpoints.
- In cases where commercial system other than available commercial BWI RF systems are used for repeat ablation during blanking, these subjects will be excluded from the long-term effectiveness analyses unless already failed long-term effectiveness endpoints prior to the repeat ablation.

#### **7.1.4 Handelling Subjects in PVI Durability Subset with Specific Ablation Scenarios in Effectiveness Endpoints Analysis**

Subjects in the PVI durability subset that receive PV ablations during the re-map visit will be included in different analyses according to the following guidelines:

For the analysis of Repeat Procedure:

- When an ablation takes place according to the remap results at the PVI durability visit and in the absence of atrial fibrillation (AF), atrial tachycardia (AT), or atrial flutter (AFL, of unknown origin\*), the subjects will not be reported as having a repeat procedure for the repeat ablation procedures related analysis.

For the long-term effectiveness endpoint including Repeat Procedure Failure:

- In cases where a PVI durability visit occurs after 90 days with an ablation for atrial fibrillation (AF), atrial tachycardia (AT), or atrial flutter (AFL, of unknown origin\*) takes place, the subjects will be considered a repeat failure.
- In cases where a PVI durability visit occurs during blanking with an ablation for atrial fibrillation (AF), atrial tachycardia (AT), or atrial flutter (AFL, of unknown origin\*) takes place, the subject will not be considered a repeat

failure. The subject will require >1 repeat ablations at blanking to be considered a repeat failure.

Note: Subjects in the PVI durability subset will be considered LTE failures ONLY IF with a proof of AF,AT or AFL confirmed by electrographic documentation or entrainment maneuvers during the durability assessment. If the ablations are performed due to non-isolated regions in the PV without proof of AF/AT/AFL it will not be considered a repeat procedure.

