7.3.3 Additional Effectiveness Endpoints

PVI Durability Rate

- Percentage of targeted PVs in the index ablation procedure being durably isolated as confirmed by the electroanatomical mapping 75 days (+/- 15days) post index ablation procedure.
- Percentage of subjects with durably isolated targeted PVs as confirmed by the electroanatomical mapping at 75 days (+/- 15days) post index ablation procedure.

Single Procedural Success: defined as freedom from documented symptomatic atrial arrhythmia (AF, AT or AFL of unknown origin*) episodes based on electrocardiographic data (≥ 30 seconds on arrhythmia monitoring device) during the effectiveness evaluation period (Day 91-Day 365) following a single index ablation procedure.

Freedom from documented symptomatic atrial arrhythmia (AF, AT or AFL of unknown origin *) episodes based on electrocardiographic data (≥ 30 seconds on arrhythmia monitoring device) during the effectiveness evaluation period (Day 91-Day 365). Acute procedural failure will also be considered failure of 12-month symptomatic recurrence free endpoint.

Freedom from documented (symptomatic and asymptomatic) atrial arrhythmia (AF, AT or AFL of unknown origin*) episodes based on electrocardiographic data (≥ 30 seconds on arrhythmia monitoring device) during the effectiveness evaluation period (Day 91-Day 365) with extra failure modes. A subject who meets any of the following criteria will also be deemed an effectiveness failure:

- Failure to achieve acute procedural success.
- Taking a new Antiarrhythmic Drug (AAD) (Class I / Class III) for atrial tachyarrhythmia (AF, AT or AFL of unknown origin*) or taking a previously failed Class I/III AAD at a greater than the highest ineffective historical dose for AF/AFL/AT during the effectiveness evaluation period (Day of 3-month visit – Day 365).
- Greater than 1 repeat ablation for AF/AT or AFL of unknown origin* in the blanking period or any repeat ablation for AF/AT or AFL of unknown origin* during the effectiveness evaluation period.

Use of a non-study device for the purpose of:

- PVI (i.e., touch-up) among all clinically relevant targeted PVs and by subject
- Ablation of left atrial non-PV AF targets (i.e., posterior wall) during index ablation procedure or for repeat procedures during blanking period.

Acute reconnection identified by adenosine/isoproterenol challenge among all clinically relevant targeted PVs

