- A repeat electro anatomical creation of a paced activation map and bipolar voltage map will be performed by the ablating physician* in the enrolling hospital at 75 days (+/-15days) post index ablation procedure to verify isolation durability of the treated pulmonary vein during the index ablation procedure.
- A BWI multi-electrode mapping catheter should be used for the remap procedure. It is **REQUIRED** to use the same mapping catheter that was used during the index ablation procedure.
- Additional ablations may be performed at the discretion of the investigator.
- **NOTE***: preference to have the PVI durability assessment performed by the same ablation physician that treated the subject during index ablation procedure.

- **Quality of life** via the Atrial Fibrillation Effect on Quality-of-Life (AFEQT™) questionnaire (non-SOC), at Month 3, 6 and 12. **NOTE:** Patient questionnaires will only be used in countries with validated languages.

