##### 7.4.4.3 Additional Effectiveness Endpoints

- **Single Procedural Success:** defined as freedom from documented symptomatic atrial arrhythmia (AF, AT or AFL of unknown origin\*) episodes based on electrocardiographic data ( $\geq 30$  seconds on arrhythmia monitoring device) during the effectiveness evaluation period (Day 91-Day 365) following a single index ablation procedure. Subjects who had repeat procedure(s) for the study arrhythmia post the index procedure will be deemed failures of this endpoint.
- **Freedom from documented symptomatic atrial arrhythmia (AF, AT or AFL of unknown origin\*):** defined as freedom from the documented symptomatic atrial arrhythmia (AF, AT or AFL of unknown origin\*) recurrence

based on electrocardiographic data ( $\geq 30$  seconds on arrhythmia monitoring device) during the effectiveness evaluation period (Day 91-Day 365).

Acute procedural failure (i.e., failure to confirm entrance block in all PVs except those that are silent and/or cannot be cannulated post-procedure, use of non-study catheter for PV isolation, and failure to have energy delivery with the study device due to ablation system malfunctions) will also be considered a failure.

- **Freedom from documented (symptomatic and asymptomatic) atrial arrhythmia (AF, AT or AFL of unknown origin\*) with additional failure modes:** defined as freedom from documented (symptomatic and asymptomatic) atrial arrhythmia (AF, AT or AFL of unknown origin\*) based on electrocardiographic data ( $\geq 30$  seconds on arrhythmia monitoring device) during the effectiveness evaluation period (Day 91-Day 365). The following criteria will also be deemed failures:
  - Failure to achieve acute procedural success.
  - Taking a new Antiarrhythmic Drug (AAD) (Class I / Class III) for atrial tachyarrhythmia (AF, AT or AFL of unknown origin\*) or taking a previously failed Class I/III AAD at a greater than the highest ineffective historical dose for AF/AFL/AT during the effectiveness evaluation period (Day of 3-month visit\* – Day 365).
  - Greater than 1 repeat ablation for AF/AT or AFL of unknown origin\* in the blanking period or any repeat ablation for AF/AT or AFL of unknown origin\* during the effectiveness evaluation period.

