### **7.11.3 Additional Effectiveness Endpoints**

The additional effectiveness endpoints will be summarized descriptively in the PP and mITT analysis sets after all study subjects completed their 12-month follow up.

- **Single Procedural Success:** The number and percentage of subjects with single procedural success will be summarized. Kaplan-Meier estimates and plots will be used to characterize the time to first documented symptomatic atrial arrhythmia (AF, AT or AFL) recurrence following a single index ablation procedure.
- **Freedom from documented symptomatic atrial arrhythmia (AF, AT or AFL of unknown origin\*):** Kaplan-Meier estimates and plots will be used to characterize the time to first documented symptomatic atrial arrhythmia (AF, AT or AFL of unknown origin\*) recurrence based on electrocardiographic data ( $\geq 30$  seconds on arrhythmia monitoring device) during the effectiveness evaluation period (Day 91-Day 365).
- **Freedom from documented (symptomatic and asymptomatic) atrial arrhythmia (AF, AT or AFL of unknown origin\*) with additional failure modes:** Kaplan-Meier estimates and plots will be used to characterize the time to first documented (symptomatic and asymptomatic) atrial arrhythmia (AF, AT or AFL of unknown origin\*) based on electrocardiographic data ( $\geq 30$  seconds on arrhythmia monitoring device) during the effectiveness evaluation period (Day 91-Day 365).

The event-free rate will also be summarized descriptively as the number and percent of subjects free from documented (symptomatic and asymptomatic) atrial arrhythmia (AF, AT or AFL of unknown origin\*) during the evaluation period.

- **Use of a non-study device:**

- The number and percentage of subjects and number and percent of PVs ablated by a non-study catheter (NSC) for PVI will be summarized.

- Rate of ablation by NSC for PVI among all targeted pulmonary veins during index procedure:

$$= \frac{\text{Number of PVs ablated by NSC}}{\text{Number of ablated PVs}}$$

- Rate of ablation by NSC for PVI among subjects during index procedure:

$$= \frac{\text{Number of subjects with at least one PV ablated by NSC}}{\text{Total number of subjects ablated for PVI}}$$

- Ablation of left atrial non-PV AF targets (i.e., posterior wall) during index ablation procedure or for repeat procedures during the blanking period.

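### Single Procedural Success, as the SAP defines it, counts a subject re-ablated for PV gaps at the durability remap as a single-procedure success

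*SAP*

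**What the plan says.** Protocol 7.3.3 defines Single Procedural Success as no documented symptomatic AF, AT or AFL of unknown origin on Day 91-365 "following a single index ablation procedure". It contains no rule for a second ablation. SAP 7.4.4.3 adds one: "Subjects who had repeat procedure(s) for the study arrhythmia post the index procedure will be deemed failures of this endpoint". SAP 7.11.3 summarises the endpoint as a number and percentage and by Kaplan-Meier, in the PP and mITT sets. The curve's event is the first symptomatic "recurrence following a single index ablation procedure".

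The remap creates an occasion for a second ablation. Protocol 7.2.4 states: "A subset of 30 study subjects will be enrolled in the PVI Durability subset". These subjects are remapped 75 days (±15) after the index procedure. Protocol 13.5.2 says of that visit: "Additional ablations may be performed at the discretion of the investigator".

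SAP 7.1.4 says how such ablations are counted. Without AF, AT or AFL, "the subjects will not be reported as having a repeat procedure for the repeat ablation procedures related analysis". The section's closing Note repeats this: "If the ablations are performed due to non-isolated regions in the PV without proof of AF/AT/AFL it will not be considered a repeat procedure". The first rule stands under the repeat-procedure analysis. The Note follows the rules for long-term effectiveness with repeat-procedure failure. Single Procedural Success is named in neither place.

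**The concern.** The endpoint is there to show what one procedure achieves. A subject whose PV gaps were closed at a second session has had two. If that subject then stays free of symptomatic arrhythmia, the outcome follows both sessions, yet it enters the numerator of a rate labelled single-procedure.

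A reader of the final report could not see this. SAP 7.12.1 reports the "Percentage of subjects with durably isolated targeted PVs, as confirmed by the electroanatomical mapping", but no planned table gives the number re-ablated at the remap or says how they were classified for this endpoint. Nothing confirmatory is at stake: SAP 7.4.4 and 7.11 state that no formal hypothesis is attached to the additional endpoints. What is at stake is the meaning of one descriptive rate and one curve.

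**Working it through.** The plan states no rate, sample size or power for this endpoint, so there is no figure of its own to reproduce.

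**Step 1: apply the rules to one subject.** A durability-subset subject has the index ablation, a remap that shows a PV gap, gap ablation with no proof of AF/AT/AFL, and no symptomatic recurrence on Day 91-365.
- Symptom criterion (Protocol 7.3.3, SAP 7.4.4.3): met.
- Failure rule (SAP 7.4.4.3): applies only to a repeat procedure for the study arrhythmia. A gap ablation without arrhythmia is not one.
- SAP 7.1.4 Note: the ablation is not a repeat procedure at all.
- Result: success, after two ablation sessions.

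**Step 2: timing.** 75 − 15 = Day 60 and 75 + 15 = Day 90. An in-window re-ablation therefore precedes the whole Day 91-365 window, and all the follow-up that counts comes after the second session. Since no recurrence counts before Day 91, censoring at an in-window remap removes the subject before any counted event and is the same as exclusion.

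**Step 3: exposure.** The subset has 30 subjects (Protocol 7.2.4) and the study 135 (SAP 6). 30/135 = 22.2%, and 1/135 = 0.74 points per subject. The PP and mITT denominators may be smaller, which would make each subject count slightly more.

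**Step 4: effect of the counting rule.** Let S be the successes as now defined, k the number re-ablated at the remap, and s the number of those k who count as successes.
- As defined: S/135
- Excluded: (S − s)/(135 − k)
- Counted as failures: (S − s)/135

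The documents give none of S, k or s. The table assumes s = k, the case with the largest effect, and two values of S: 88 (65.2%, close to the 65% that SAP 6 assumes for a different endpoint, the 12-month secondary) and 108 (80.0%, a higher alternative).

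| k | S = 88: excluded | S = 88: failures | S = 108: excluded | S = 108: failures |
|---|---|---|---|---|
| 3 | 85/132 = 64.4% | 85/135 = 63.0% | 105/132 = 79.5% | 105/135 = 77.8% |
| 12 | 76/123 = 61.8% | 76/135 = 56.3% | 96/123 = 78.0% | 96/135 = 71.1% |
| 30 | 58/105 = 55.2% | 58/135 = 43.0% | 78/105 = 74.3% | 78/135 = 57.8% |

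The k = 30 row is an extreme: every subset subject re-ablated and every one a success.

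Counting these subjects as failures can only lower the rate or leave it unchanged. Exclusion can move it either way, and lowers it only if s/k exceeds S/135. With S = 88, k = 12 and s = 6, for example, exclusion gives 82/123 = 66.7%, above 65.2%.

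**The case against.** The strongest reply is that the SAP is not silent. Its two rules give a determinate answer. Section 7.1.4 is titled for effectiveness endpoints in general, and its Note names no endpoint. The revision history records that the section was clarified in V2.0 for different durability scenarios. This looks like a deliberate choice, and a defensible one: the remap is required by the study, and an arrhythmia-free subject outside the subset would have no protocol remap at which a gap could be found. Most of this stands. A reader might infer that the plan has no rule here, but the documents do not support that. The difficulty is that the stated rules, combined, do not fit the endpoint's description.

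A second reply is that counting these subjects as failures has its own bias. It penalises only those given a research remap, while subjects with the same gaps among the other 105 (135 − 30) remain successes. This also stands. A reader might infer from the endpoint's name that any second ablation must be a failure, but the Protocol nowhere says so. Failure is therefore not proposed as the main rule.

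Third, it is tempting to treat the non-durable count from SAP 7.12.1 as a ceiling on the number re-ablated. It is not a strict bound. The PVI Durability Analysis Set (SAP 5) requires a readable index map and a map within 75 ± 15 days, whereas SAP 7.1.4 itself foresees durability visits after Day 90. Protocol 13.5.2 also does not confine ablation at the remap to reconnected veins.

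None of these replies answers the case for showing the rate with and without the affected subjects, and for stating how many there were.

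**Conclusion.** The concern holds in this limited form. Following the SAP exactly places some twice-ablated subjects among the single-procedure successes, and neither the proportion nor the Kaplan-Meier curve separates them. At most 30 subjects are affected. Measured against a failure rule, the rate could be higher by anything from 0 to 22.2 points, taking 135 as the denominator. Where in that range the trial will fall cannot be said, because the documents give no re-ablation rate; the scenarios above are illustrations only.

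A reader might infer that the trial's formal conclusions are weakened. They are not: the two primary tests, the secondary test, alpha, power and the study-success criterion do not use this endpoint. Minor.

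**What to change.** In SAP 7.4.4.3 and 7.11.3, state that Single Procedural Success will be reported, as a proportion and by Kaplan-Meier in both PP and mITT, in two ways: as now defined, and with subjects who had any left-atrial re-ablation at the remap excluded. A version counting them as failures may be added as a conservative bound, with a note that it penalises only subjects given a study-mandated remap.

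Report the number of remap-only re-ablations on its own line beside the repeat-ablation rates, whose definition stays as it is. Add a cross-reference in SAP 7.1.4 so that its Note does not contradict the new text. Nothing changes in what investigators may do at the remap.

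The cost is short text edits in three SAP sections, a few extra rows and one extra curve per analysis set, and no data beyond the remap ablation record. The sponsor also accepts that the additional single-procedure rate may be less favourable.

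Two cautions belong in the table notes. PV gaps plausibly predict recurrence, so exclusion may be informative. For a remap performed after Day 90, censoring and exclusion are no longer the same, so the text should say which is used.
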